11.1.3 Measurable Disease

Patients enrolled on the CLEVER trial will have completed surgery for their primary breast tumor and be free of overt metastatic disease. Thus there is no tumor to measure for the effect of the study therapy. Rather, the goal of this trial is to eradicate minimal residual disease, in the form of disseminated tumor cells (DTCs) that are present in the bone marrow. Therefore, bone marrow DTCs constitute the "measurable" disease in this trial. A patient will be classified as having "measurable disease" if at least 1 disseminated tumor cell (DTC) is detected

in 5 ml of bone marrow aspirate by immunohistochemistry, as described in section 13.2.1.

11.2 Guidelines for Evaluation of Disease

11.2.1 Measurement Methods

Bone marrow aspirate will be used to obtain sample for assessment of DTCs. This will be performed in a standard fashion as outlined in section 13. Bone marrow will be assayed for DTCs by standard immunohistochemical assay performed under CLIA conditions in the Clinical Pathology Laboratory at the University of Pennsylvania as described in section 13.

11.2.2 Response Criteria

Response in this trial will be performed in all patients, and is defined by the change in detectable DTC number (# cell/5 ml marrow aspirate) from baseline to each timepoint. We will define “response” for each patient as a 50% or greater decrease in DTC number at each treatment time point compared to baseline. The interventional arm will be considered successful if at least 20% of patients experience this predefined response endpoint. We anticipate that the baseline variability in DTC measurement will lead to no more than a 4% response rate in the absence of treatment (null rate). The efficacy objective of this trial (a secondary objective) is to evaluate the preliminary efficacy of EVE, HCQ or the combination in reducing or eliminating breast cancer DTCs, and provide estimates of effect for future definitive trials. The primary measure of efficacy in this trial is change in the number of detectable disseminated tumor cells (DTCs) in the bone marrow of patients on study. DTCs will be detected from 5 ml of bone marrow extracted from the posterior iliac crest at baseline (pre-treatment), after 3 cycles, 6 cycles, and 12 cycles (if applicable) of study treatment, and at 6 months after the last dose of study treatment (optional).

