5. Bone marrow aspirate performed at the end observation (before the start of therapy), at the end of C3 (between D23-28), at the end of C6 (between D23-21 days after last dose IP therapy), and, if patient continued on additional treatment, at the end of C12, (between D23-21 days after last dose IP therapy).
6. Blood collected for ptDNA and CTCs pretreatment and at the completion of observation (before the start of therapy), at the completion of C3 (before the start of C4), at the completion of C6 (within 21 days of last dose), and at completion of C12 (within 21 days of last dose).
7. Baseline bone marrow aspirate positive for DTCs must have been done within 6 months of the screening phase.
8. Participants who clear DTCs from the bone marrow (i.e., negative DTC-IHC test) after 6 or 12 cycles of therapy will have optional bone marrow aspirate collected for retesting at the first 6 month follow up visit.

Note: Additional tests may be performed at the discretion of the treating investigator as clinically indicated. The sample collection schedules outlined above are based on an ideal subject. The sample schedule should be followed as closely as is realistically possible; however, the schedule may be modified due to problems such as scheduling delays or conflicts (e.g., clinic closure, poor weather conditions, vacations, etc.)

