5.2 Screening Phase

Patients found to have detectable DTCs by immunohistochemistry, through the PENN-SURMOUNT Screening study (UPCC 28115; IRB# 824098) or other studies will be screened for trial participation during the screening phase. This will include assessments of medical history, overall physical condition, physical exam, baseline laboratory studies, and symptom-directed imaging (if applicable) to rule out the presence of overt metastatic disease, per NCCN guidelines. Patients will undergo a baseline bone marrow aspirate if their prior bone marrow aspirate detecting DTCs occurred > 6 months prior to the screening phase. If a bone marrow aspirate positive for DTCs occurred ≤ 6 months prior to screening, this will not be repeated, and the prior DTC count will provide the baseline DTC assessment.

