7 TREATMENT PLAN

This is a randomized, controlled, open label pilot trial. A total of 60 patients

will be enrolled, with at least 15 patients allocated to each treatment group (Arms C and D constituting the same treatment group). The initial treatment period is 6 months (24 weeks). During the initial treatment period, patients will be randomized to one of 4 arms: HCQ alone (Arm A), EVE alone (Arm B), combination HCQ and EVE (Arm C) – Arm C is closing to accrual with Amendment 7 – or control/delayed combination HCQ and EVE (Arm D). Starting with Amendment 7, patients who would have been allocated to Arm C will be redirected to Arm D in order to increase the number of patients with repeat DTC assessments to aid assay reproducibility analysis. At the conclusion of 3 cycles of therapy (Arms A, B, and C) or 3 cycles of observation (Arm D), patients will undergo repeat bone marrow aspirate. Patients on Arm D will then commence combination therapy with HCQ + EVE for 6 cycles (24 weeks). After 3 cycles of therapy, patients on Arm D will undergo another bone marrow aspirate. After 6 cycles of therapy, patients on all arms will undergo another bone marrow aspirate. Patients with a negative bone marrow aspirate for DTCs at after cycle 6 will have all therapy discontinued and enter the follow up phase. Patients who have persistently positive bone marrow DTCs will be continued on combination HCQ + EVE for an additional 6 cycles (24 weeks). At the conclusion of this combination treatment period (cycle 12), all treatment will be discontinued and a bone marrow aspirate will be performed.

Patients will be evaluated at the initiation of every cycle for adverse events, and dose reductions will be employed for toxicity. Patients will continue to be followed for recurrence events for 3 years after completion of treatment.

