7.1 Study Arms

Patients will be randomized during the Screening Phase to one of four investigational arms. These are shown in the schema above and detailed as follows (Note that Arm C is closing with Amendment 7):

Arm A: Patients will receive HCQ, 600 mg BID, for 24 weeks. If they are determined to have detectable DTCs after week 24, they will be crossed over to combination therapy, in which they will continue HCQ, 600 mg BID and add EVE, 10 mg daily for an additional 24 weeks.

Arm B: Patients will receive EVE, 10 mg daily, for 24 weeks. If they are determined to have detectable DTCs after week 24, they will be crossed over to combination therapy, in which they will continue EVE, 10 mg daily and add HCQ, 600 mg BID, for an additional 24 weeks.

Arm C: Patients will receive the combination of HCQ, 600 mg BID, and EVE, 10 mg daily, for 24 weeks. If they are determined to have detectable DTCs after week 24, they will continue combination HCQ/EVE therapy for an additional 24 weeks. Arm C is closing with Amendment 7. Patients randomized after Amendment 7 who would have been assigned to Arm C will be redirected to Arm D.

Arm D: Patients will be observed for 12 weeks without study therapy. At the completion of the observation period, they will receive combination therapy of HCQ, 600 mg BID and EVE, 10 mg daily for 24 weeks. If they are determined to have detectable DTCs after week 24, they will continue combination HCQ/EVE therapy for an additional 24 weeks.

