#### Bayesian Poisson regression model

The number of DTCs observed by visit for each patient was analyzed with a Bayesian Poisson regression model that included treatment-by-visit effects and patient-level random intercepts to account for overdispersion in the outcomes. We denote observations within index  $i \in 1, ..., N$  and patients with index  $s[i] \in 1, ..., S$ . Let  $y_i$  represent the number of DTCs for observation i. The Bayesian model is specified as follows:

$$y_i \sim Pois(\lambda_i)$$
  
 $\log(\lambda_i) = \alpha + \mu_{s[i]} + X'_i \beta$ 

where  $\alpha$  is an overall intercept,  $\mu_{s[i]}$  is a patient-level intercept,  $X_i$  is a vector of treatment by visit effects, and  $\beta$  is a vector of treatment effects by visit. The following non-informative prior distributions are specified on the unknown model parameters:

$$\alpha \sim N(0, 10^2)$$
  
 $\beta_j \sim N(0, 10^2), j = 1:j$   
 $\mu_s \sim N(0, \sigma^2), s = 1:S$   
 $\sigma \sim t_3^+(0, 1)$ 

Posterior sampling was done using the *brms* package (version 2.19.0) in the R programming language (version 4.3.1). Treatment effects for HCQ, EVE, and HCQ + EVE are presented by visit as the percent reduction in mean DTCs compared to observation alone at C3. Combination effects are evaluated by comparing the mean number of DTCs with HCQ + EVE to HCQ and EVE alone by visit. The estimated probability of DTC clearance is presented by visit and treatment group. Summaries of model parameters include the posterior mean, median, standard deviation (SD), and 95% credible interval (CrI).

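### Arm D's response to HCQ + EVE is scored from a marrow taken before 12 untreated weeks, so a DTC fall that precedes the first dose can count as a drug response

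*Protocol*

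**What the plan says.** **Response.** Protocol 11.2.2 and 12.2.2 define response as a "50% or greater decrease in DTC number at each treatment time point compared to baseline". An arm succeeds if at least 3 of 15 patients respond. The untreated response rate is expected to be no more than 4%.

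**Baseline.** The study calendar (5.1, Table 2) labels the screening column as baseline. Footnote 7 reads "Baseline bone marrow aspirate positive for DTCs must have been done within 6 months of the screening phase". Where a positive marrow of that age exists, 5.2 says "this will not be repeated, and the prior DTC count will provide the baseline DTC assessment". Neither section treats Arm D differently.

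**Arm D.** Section 7.1 says "Patients will be observed for 12 weeks without study therapy". A marrow is taken at the end of observation, before therapy starts (Table 2 footnote 5; 5.3). Its result is not returned to patients, and combination therapy follows with no condition on it. Its stated uses are the 3-month untreated comparison (2.2.2) and assay reproducibility (section 7). The marrows listed for response in 11.2.2 are those "at baseline (pre-treatment), after 3 cycles, 6 cycles, and 12 cycles (if applicable) of study treatment", which does not name the end-of-observation sample.

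**Evaluability.** Section 11.1.2 requires DTCs at baseline, not at first dose.

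**Analysis.** Section 7 describes "Arms C and D constituting the same treatment group" and, from Amendment 7, sends patients due for Arm C to Arm D. The SAP states: "Combination effects are evaluated by comparing the mean number of DTCs with HCQ + EVE to HCQ and EVE alone by visit".

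**The concern.** Arm D has two roles: untreated control for 12 weeks, then combination therapy. The screening marrow is the right reference for the first role. For the second it precedes treatment by at least 12 weeks, and the response rule does not separate what happened before the first dose from what happened after it. A patient with no detectable DTC at first dose, and none at C3 or C6, meets the response definition although there was nothing detectable left for the drugs to reduce.

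This bears on two secondary objectives in 2.2.2: the activity of the combination, and its incremental benefit over single agents. After Amendment 7 all newly randomised combination patients come through Arm D, so the affected share of combination data grows.

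**Working it through.** **1. Which marrow is the reference?** Three places point to screening: the calendar's column label, footnote 7, and the sentence in 5.2 that names the prior count. Footnote 6 also lists the pretreatment blood sample and the end-of-observation blood sample as two separate items, so the protocol does not use pretreatment to mean end of observation there. No sentence resets baseline for Arm D.

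**2. Age of the reference at first dose.** Taking 6 months as 183 days, plus the 30-day screening window:
- Arms A to C: 183 + 30 = about 213 days at most.
- Arm D: 183 + 30 + 84 = about 297 days at most.

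**3. The plan's own rule.** With X binomial (n = 15, p), P(X ≥ 3) = 1 − Σ C(15,x) p^x (1 − p)^(15 − x) over x = 0, 1, 2. At p = 0.04 this is 1 − (0.5421 + 0.3388 + 0.0988) = 0.0203, or 2.0%. At p = 0.20 it is 60.2%, which does not reproduce the approximately 80% power stated in 12.2.2. That is a separate matter and does not affect this point.

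**4. Adding a pre-dose fall.** Let q be the share of patients whose DTCs fall by at least half before the first dose and stay down. The documents give no value, so q is an assumption. With an inactive regimen, p = 1 − (1 − 0.04)(1 − q).

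| q (assumed) | p | Expected responders of 15 | P(at least 3 of 15) |
|---|---|---|---|
| 0 | 0.040 | 0.60 | 2.0% |
| 5% | 0.088 | 1.32 | 14.0% |
| 10% | 0.136 | 2.04 | 33.4% |
| 20% | 0.232 | 3.48 | 71.2% |

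The table treats all 15 patients as Arm D patients. Any Arm C patients in the group dilute the effect.

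**5. What a reset does and does not do.** Counts were simulated with no drug effect and no true decline, requiring at least 1 DTC at screening. The count distributions are assumptions.

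| Count distribution | Response from screening | Reset, negatives at end of observation excluded | Reset, negatives kept as non-responders |
|---|---|---|---|
| Poisson, mean 2 | 37.0% | 37.0% | 31.9% |
| Gamma-Poisson, mean 3, shape 0.5 | 31.8% | 26.4% | 22.2% |

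In this setting Arms A and B, scored from screening, have the same rate as Arm D scored from screening. Resetting removes a real pre-dose decline but not counting noise. It can also set Arm D below A and B, because Arm D then needs a second positive marrow.

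**6. Visit timing.** Arm D's C3 and C6 marrows fall about 12 + 12 = 24 and 12 + 24 = 36 weeks after observation starts. In Arms A to C they fall at about 12 and 24 weeks.

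**The case against.** **Baseline may have been meant differently.** Sections 2.2.2 and 11.2.2 gloss baseline as pre-treatment, and the end-of-observation marrow is also taken before treatment. The sponsor may have intended it. The gloss is loose enough to allow that, but 5.2 and footnotes 6 and 7 point the other way. If it was the intention, the text still has to say so.

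**The 4% null already allows for untreated response.** It does, but 11.2.2 and 12.2.2 attribute it to variability in the baseline measurement. It makes no stated provision for a true change over 12 untreated weeks.

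**A reset is not neutral.** This stands. Against Arms A and B the screening reference is the like-for-like one, and a single zero on an assay that 3.3.1 calls relatively insensitive does not prove clearance. Both references are therefore needed.

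**The endpoint is secondary, in a feasibility pilot.** This also stands and limits the weight of the point.

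**Stronger readings that the documents do not support.** A reader might infer that Arms C and D are pooled for DTC response. The only stated permission to combine them for analysis is for feasibility (12.2.1), and the percent-change regression in 12.2.2 uses indicators for three active treatments against the delayed arm. A reader might also infer that the SAP model carries the same responder error, or that its combination contrast is biased by a calculable amount. The model's treatment effects are set against observation at C3 and do not use the responder rule. The SAP does not say whether Arm C and Arm D on-treatment visits share a cell, so no figure can be put on that contrast.

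**Conclusion.** The point holds for the protocol's response rule. As written, Arm D's response to HCQ + EVE is measured from screening, and a durable fall before the first dose counts as a response. Its size depends on an untreated rate that the documents do not give. For an assumed q of 5% to 20%, the chance that an inactive regimen passes the 3-of-15 rule rises from 2.0% to between 14% and 71%. This takes the 4% null as given and all 15 patients as Arm D patients. An early faller counts only if still at least 50% down at a treatment time point. If DTCs tend to rise untreated, the rule understates the combination instead. The primary feasibility endpoint is not affected. For the SAP, what can be said is that the handling of Arm D's later on-treatment visits is not stated.

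**What to change.** In Protocol 11.2.2 and 12.2.2, and where noted in the SAP:

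1. Measure Arm D's untreated 3-month change from the screening marrow.
2. Judge Arm D's response to HCQ + EVE, including the 3-of-15 rule, from the end-of-observation marrow. Report patients with no DTC at that marrow as a separate category, and state the denominator. Give the screening-based result alongside as a sensitivity analysis for comparison with Arms A and B.
3. Report Arm C and Arm D on-treatment DTC results separately before any pooling. State in the SAP whether Arm D's on-treatment visits are their own treatment-by-visit cells, given the 12-week difference in time since randomisation.
4. Limit any randomised contrast of Arm C with A or B to patients randomised while Arm C was open, since the plan continues A and B after Arm C closes.

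**Cost.** No new marrow is needed. Fewer Arm D patients may count as responders, and one sensitivity table is added. The SAP describes the modelling as already done, so anything added now should be dated and labelled as such.

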12 STATISTICAL CONSIDERATIONS AND METHODOLOGY

12.1 Sample Size

The primary endpoint of this pilot study is feasibility. 60 patients will be enrolled on the trial. Based on the literature and our preliminary experience, we anticipate detecting BM-DTCs in 20 - 25% of the patients we screen on the PENN-SURMOUNT study (IRB# 824098/UPCC 28115), thus have planned to screen 250 - 300 patients over three years, allowing for refusals and drop-out.

12.2 Analysis Plan

12.2.1 Primary Endpoint

The phase II trial endpoint “feasibility” is based upon the overall safety and tolerability of the treatment arms, and will be defined as at least 11 of 15 patients within each treatment group completing 6 cycles of therapy without grade 3 or 4 toxicity. When evaluating feasibility of the combination therapy, Arm C and D may be combined for analysis, since both arms receive the same study treatment (Arm D is just a delayed start). Toxicity will be determined by NCI CTCAE v4 criteria, and categorized by system and grade. Patients who drop out before the 6-month time

point for reasons other than toxicity and not related to feasibility will be replaced. With 15 patients per group, an exact 95% confidence interval around the feasibility and toxicity rates will be no more than 0.52 units wide. Arms that are discontinued for lack of feasibility will be dropped from the trial, but others may continue, so long as they remain “feasible” by this definition.

Because this is a potentially curable patient population, we will also institute an early stopping rule, should the toxicity rates exceed those expected or acceptable in this setting. To do this, we will implement a Bayesian toxicity monitoring approach with a target protocol-defined DLT rate of 30%. We assume a $Beta(1,2)$ prior, equivalent to one DLT observed in 3 treated patients. Early termination for toxicity will be considered based on a posterior probability that the toxicity rate exceeds 30%. Early termination will be considered if DLT is observed in 2 of 3 patients (0.84 posterior probability), 3 of 6 patients (0.81), 4 of 9 patients (0.79), 5 of 12 patients (0.78), 6 of 15 patients (0.78).

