1 STUDY SUMMARY

Title	A Phase II Pilot Trial of Hydroxychloroquine, Everolimus or the Combination for Prevention of Recurrent Breast Cancer
Short Title	CLEVER Pilot Trial
Protocol Number	IRB #826253; UPCC 24116
Methodology	
This is a randomized, controlled, open label pilot trial. A total of 60 patients will be enrolled, with 15 patients allocated to each treatment arm. Patients will be evaluated at the initiation of every cycle for adverse events, and dose reduction will be employed for toxicity. Bone marrow aspiration will be performed at the end of cycle 3, cycle 6, and if patient continued on second treatment phase, at the end of cycle 12. The initial six-month study period is designed to assess the effects of HCQ, EVE and their combination. After three months of observation, control patients will be offered HCQ/EVE investigational therapy for six cycles; thus, the control group is actually a delayed treatment group and all patients will receive treatment. Patients who continue to demonstrate positive bone marrow DTCs after six cycles will be offered the opportunity to continue on combination therapy for an additional 6 cycles. Patients will continue to be followed for recurrence events for up to 3 years after completion of treatment.

Study Duration	Active Enrollment: 3 years; Follow-up: 3 years
Study Center(s)	The University of Pennsylvania and affiliated sites
Objectives	
Primary Clinical Objective: To evaluate the feasibility of administering HCQ, EVE or the combination in patients who have completed primary therapy for breast cancer and harbor bone marrow disseminated tumor cells
 
Endpoint: $\geq 75\%$ of patients in each arm reaching the 6-month evaluation time point without grade 3 or 4 toxicity.
 
Secondary Clinical Objectives:
 
1. To determine the safety of administering HCQ + EVE in combination with adjuvant endocrine therapy
 
Endpoints Incidence of adverse events within each treatment stratum and dose level by NCI CTCAE v4 criteria.
 
2. To evaluate preliminary efficacy of HCQ, EVE or the combination in reducing or eliminating DTCs
 
Endpoint

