	
of adjuvant endocrine and bone modifying agents is allowed per standard of care guidelines.
 
 • Bone marrow aspirate after completion of therapy demonstrates detectable DTCs (via IHC) • No evidence of recurrent local or distant breast cancer by physical examination, blood tests (CBC, LFTs, Alk Phos), or symptom-directed imaging, per NCCN guidelines. • Age \geq 18 years • ECOG performance status \leq 2 • No contraindications to the study medications or uncontrolled medical illness. • Adequate bone marrow function as shown by: ANC \geq 1.5 x 10⁹/L, Platelets \geq 100 x 10⁹/L, Hb >9 g/dL • Adequate liver function as shown by: Serum bilirubin \leq 1.5 x ULN, ALT and AST \leq 2.5 x ULN, and INR \leq 1.5 • Anticoagulation is allowed if target INR \leq 1.5 on a stable dose of warfarin or on a stable dose of anticoagulant for >2 weeks at time of randomization. For patients on therapeutic anti-coagulants, medication must be clinically held peri-procedure (bone marrow aspirate) per standard clinical management. • Adequate renal function: serum creatinine \leq 2.0 x ULN or creatinine clearance (CrCl) \geq 30mL/min obtained within 28 days prior to registration. A calculated creatinine clearance by Cockcroft-Gault Formula is acceptable in lieu of a measured value. • Serum cholesterol \leq300 mg/dL OR \leq7.75 mmol/L AND triglycerides \leq 2.5 x ULN. NOTE: In case one or both of these thresholds are exceeded, a fasting lipid assessment will be ordered. If one or both of these thresholds are still exceeded in a fasting state, the patient can only be included after initiation of appropriate lipid lowering medication. • Ability to provide informed consent

Statistical Methodology
	
The primary endpoint of this pilot study is feasibility. The secondary endpoints are tolerability and the measured effect of the investigational therapy on DTCs in patients with measureable DTCs at baseline and the comparison of this effect to that in a control population. Because this is proof-of-concept, sample sizes are not sufficient to address long-term recurrence risk. Randomization is being performed to minimize uncontrolled confounding.
 
The trial endpoint “feasibility” will be defined as at least 11 of 15 patients within each treatment regimen completing 6 cycles of therapy without grade 3 or 4 toxicity. While arms may be

[figure not shown]

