2 STUDY OBJECTIVES

2.1 Primary Clinical Objective: To evaluate the feasibility of administering HCQ, EVE or the combination in patients who have completed primary therapy for breast cancer and harbor bone marrow disseminated tumor cells

Endpoint:

- $\geq 75\%$ of patients overall completing 6 cycles of therapy without grade 3 or 4 toxicity

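### The primary feasibility criterion is stated in three incompatible ways (at least 75% in each arm, at least 75% overall, 11 of 15 = 73.3% per group), and the pooled Arm C+D group has no cut-off

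*Protocol*

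**What the plan says.** Feasibility is the primary endpoint (Protocol section 12.1), and its criterion appears in four places.

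- **Study Summary, Objectives:** at least 75% "of patients in each arm reaching the 6-month evaluation time point without grade 3 or 4 toxicity".
- **Section 2.1, Primary Clinical Objective:** at least 75% "of patients overall completing 6 cycles of therapy without grade 3 or 4 toxicity".
- **Study Summary, Statistical Methodology:** at least 11 "of 15 patients within each treatment regimen completing 6 cycles of therapy without grade 3 or 4 toxicity".
- **Section 12.2.1, Primary Endpoint:** "at least 11 of 15 patients within each treatment group completing 6 cycles of therapy without grade 3 or 4 toxicity".

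Section 12.2.1 attaches a consequence: "Arms that are discontinued for lack of feasibility will be dropped from the trial", while the remaining arms may go on as long as they meet the same definition.

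On the combination regimen, section 12.2.1 says "When evaluating feasibility of the combination therapy, Arm C and D may be combined for analysis". Section 7 describes groups of at least 15 patients, with "Arms C and D constituting the same treatment group", and redirects Arm C allocations to Arm D from Amendment 7. No section gives a required count for a denominator other than 15.

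The SAP text available covers only the DTC model ("The number of DTCs observed by visit for each patient was analyzed with a Bayesian Poisson regression model") and does not mention feasibility.

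**The concern.** The wordings differ in threshold and in unit.

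- **Threshold:** 11 of 15 is below 75%, so the statistical sections accept a result that the objectives reject.
- **Unit:** section 2.1 judges all patients together, and the other three places judge each arm, regimen or group. A good result in two regimens can then hide a poor result in the third.
- **Combination regimen:** pooling C and D is optional and the pooled cut-off is not fixed. Both choices could be made after the results are known.

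The primary result is a pass or fail count, and under section 12.2.1 failing it removes an arm. The wordings agree when every group is clearly above 75%. They part in borderline or uneven results, where a fixed rule is needed most.

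**Working it through.** **Inputs.** The 75% floor is from the Study Summary objectives and section 2.1. The count of 11 of 15 is from the Study Summary methodology and section 12.2.1. Total enrolment of 60 is from sections 7 and 12.1. The pooled size of 30 is an assumption: 60 − 15 (A) − 15 (B). The protocol gives no expected feasibility rate and no alpha or power for the rule, so true rates of 70% to 90% are assumed as a range.

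**The plan's own figure.** The Clopper-Pearson 95% interval for n = 15, maximised over all counts, is widest at 7 or 8 successes, with width 0.5215. This reproduces the stated 0.52. The precision statement is sound; the fault is in the decision rule.

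**Thresholds.**

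- n = 15: 0.75 × 15 = 11.25, so 12 are needed. 11/15 = 73.3%; 12/15 = 80.0%.
- n = 30: 0.75 × 30 = 22.5, so 23 are needed (76.7%). The 11/15 proportion gives 22 (73.3%).
- n = 60: 0.75 × 60 = 45.

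**Effect of the threshold.** Exact binomial, P(X ≥ k) for a true rate p. The column P(X = 11) is the chance that one group's verdict turns on the wording.

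| p | n=15, ≥11 | n=15, ≥12 | P(X = 11) | n=30, ≥22 | n=30, ≥23 |
|---|---|---|---|---|---|
| 0.70 | 0.5155 | 0.2969 | 0.2186 | 0.4315 | 0.2814 |
| 0.75 | 0.6865 | 0.4613 | 0.2252 | 0.6736 | 0.5143 |
| 0.80 | 0.8358 | 0.6482 | 0.1876 | 0.8713 | 0.7608 |
| 0.85 | 0.9383 | 0.8227 | 0.1156 | 0.9722 | 0.9302 |
| 0.90 | 0.9873 | 0.9444 | 0.0428 | 0.9980 | 0.9922 |

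**Effect of the unit, by example.** For simplicity take three groups of 15.

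- Successes of 10, 13 and 13 give 36/45 = 80%, which passes an overall 75% rule. The first group, at 10/15 = 66.7%, fails every per-group wording.
- Successes of 11, 11 and 11 give 33/45 = 73.3%. Section 12.2.1 is met in every group and both 75% statements fail.

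**Effect of the unit, by enumeration.** Assume independent groups of 15, 15 and 30 with one common true rate. *Overall* means at least 45 of 60. *All groups* means A ≥ 11, B ≥ 11 and C+D ≥ 22.

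| p | Overall passes | All groups pass | Overall passes, at least one group fails |
|---|---|---|---|
| 0.75 | 0.5688 | 0.3174 | 0.2594 |
| 0.80 | 0.8694 | 0.6086 | 0.2646 |
| 0.85 | 0.9864 | 0.8559 | 0.1310 |
| 0.90 | 0.9998 | 0.9728 | 0.0271 |

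**Pooled C+D.** Applying the literal count of 11 to 30 patients would mean 11/30 = 36.7%, a bar passed with probability 0.997 even at a true rate of 60%. That cannot be intended, so some scaling is needed, and the text does not say which proportion to scale.

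**The case against.** The strongest reply is that the operative rule can be identified. Both statistical sections give 11 of 15 per regimen or group, and section 12.2.1 ties the continuation of arms to its own definition. On that reading the objectives were simply not brought into line, and the threshold gap is one patient (11 or 12 of 15; 22 or 23 of 30) in an open-label pilot whose interval may be 0.52 wide. This is a fair account of which rule probably applies, but no section gives section 12.2.1 precedence over the primary objective. Rounding 11.25 down could explain the 11; it cannot explain *overall* against *each*.

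Three further points stand as limits on the size of the problem.

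- The probability of about 0.26 is not the chance that a stated trial verdict flips. The protocol judges groups separately and nowhere says that one failing group fails the trial. The figure also mixes the change of unit with the change of threshold. It shows how often an overall rule would hide a failing group.
- Disagreement is greatest near the cut-off. At a true rate of 90%, the chance of exactly 11 of 15 is 0.043 and the unit figure is 0.027.
- The missing pooled cut-off is an omission, not an arithmetic error, and the pooled size of 30 depends on accrual after Amendment 7.

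**Conclusion.** The concern holds. The primary endpoint has incompatible criteria in current text, and no rule of precedence settles them. For a group of 15, the choice between 11 and 12 changes the verdict with probability 0.19 to 0.23 at true rates of 70% to 80%, and less above that. An overall 75% rule would pass while at least one regimen failed with probability about 0.26 at true rates of 75% and 80%, under the assumed group sizes and common rate. For the pooled combination group, neither the use of pooling nor the required count is fixed. The true rates and the pooled size of 30 are assumptions. The contradiction itself rests only on the protocol's wording and on 11/15 being less than 75%. It must be fixed, because a primary decision rule needs one threshold and one unit.

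**What to change.** Use one criterion in the Study Summary (objectives and methodology), section 2.1 and section 12.2.1, and apply it per regimen: A, B, and C+D pooled. Delete the overall wording.

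- **Preferred:** keep 11 of 15, restate the target as 73%, and give 22 of 30 for pooled C+D. Nothing changes operationally for groups of 15.
- **Alternative, only if no outcome data have been seen:** keep the 75% floor and restate the count as 12 of 15, with 23 of 30 pooled. At a true rate of 80% this lowers the pass probability from 0.84 to 0.65 for a group of 15, and from 0.87 to 0.76 for 30.

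In either case, say whether C+D is the feasibility group or pooling is only optional, and how the cut-off is set for a denominator other than 15 or 30 (for example, the stated proportion rounded up). It would also help to say that six months means six cycles of treatment for Arm D, whose treatment starts after the observation period.

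The SAP excerpt is in the past tense. If the data have been analysed, declare section 12.2.1 the governing rule and report whether any regimen's verdict changes under the other wordings.

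The cost is protocol wording only. The available SAP text has nothing on feasibility that would need to change.
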